Annex 3: VAS

Female Sexual Function Index (FSFI) ©

Subject Identifier _____

Date _____

INSTRUCTIONS: These questions ask about your sexual feelings and responses during the past 4 weeks. Please answer the following questions as honestly and clearly as possible. Your responses will be kept completely confidential. In answering these questions the following definitions apply:

Sexual activity can include caressing, foreplay, masturbation and vaginal intercourse.

Sexual intercourse is defined as penile penetration (entry) of the vagina.

Sexual stimulation includes situations like foreplay with a partner, self-stimulation (masturbation), or sexual fantasy.

CHECK ONLY ONE BOX PER QUESTION.

Sexual desire or interest is a feeling that includes wanting to have a sexual experience, feeling receptive to a partner's sexual initiation, and thinking or fantasizing about having sex.

1. Over the past 4 weeks, how **often** did you feel sexual desire or interest?

- Almost always or always
- Most times (more than half the time)
- Sometimes (about half the time)
- A few times (less than half the time)
- Almost never or never

2. Over the past 4 weeks, how would you rate your **level** (degree) of sexual desire or interest?

- Very high
- High
- Moderate
- Low
- Very low or none at all

Sexual arousal is a feeling that includes both physical and mental aspects of sexual excitement. It may include feelings of warmth or tingling in the genitals, lubrication (wetness), or muscle contractions.

3. Over the past 4 weeks, how **often** did you feel sexually aroused ("turned on") during sexual activity or intercourse?

- No sexual activity
- Almost always or always
- Most times (more than half the time)
- Sometimes (about half the time)
- A few times (less than half the time)
- Almost never or never

4. Over the past 4 weeks, how would you rate your **level** of sexual arousal ("turn on") during sexual activity or intercourse?

- No sexual activity
- Very high
- High
- Moderate
- Low
- Very low or none at all

5. Over the past 4 weeks, how **confident** were you about becoming sexually aroused during sexual activity or intercourse?

- No sexual activity
- Very high confidence
- High confidence
- Moderate confidence
- Low confidence
- Very low or no confidence

6. Over the past 4 weeks, how **often** have you been satisfied with your arousal (excitement) during sexual activity or intercourse?

- No sexual activity
- Almost always or always
- Most times (more than half the time)
- Sometimes (about half the time)
- A few times (less than half the time)
- Almost never or never

7. Over the past 4 weeks, how **often** did you become lubricated ("wet") during sexual activity or intercourse?

- No sexual activity
- Almost always or always
- Most times (more than half the time)
- Sometimes (about half the time)
- A few times (less than half the time)
- Almost never or never

8. Over the past 4 weeks, how **difficult** was it to become lubricated ("wet") during sexual activity or intercourse?

- No sexual activity
- Extremely difficult or impossible
- Very difficult
- Difficult
- Slightly difficult
- Not difficult

9. Over the past 4 weeks, how often did you **maintain** your lubrication ("wetness") until completion of sexual activity or intercourse?

- No sexual activity
- Almost always or always
- Most times (more than half the time)
- Sometimes (about half the time)
- A few times (less than half the time)
- Almost never or never

10. Over the past 4 weeks, how **difficult** was it to maintain your lubrication ("wetness") until completion of sexual activity or intercourse?

- No sexual activity
- Extremely difficult or impossible
- Very difficult
- Difficult
- Slightly difficult
- Not difficult

11. Over the past 4 weeks, when you had sexual stimulation or intercourse, how **often** did you reach orgasm (climax)?

- No sexual activity
- Almost always or always
- Most times (more than half the time)
- Sometimes (about half the time)
- A few times (less than half the time)
- Almost never or never

12. Over the past 4 weeks, when you had sexual stimulation or intercourse, how **difficult** was it for you to reach orgasm (climax)?

- No sexual activity
- Extremely difficult or impossible
- Very difficult
- Difficult
- Slightly difficult
- Not difficult

13. Over the past 4 weeks, how **satisfied** were you with your ability to reach orgasm (climax) during sexual activity or intercourse?

- No sexual activity
- Very satisfied
- Moderately satisfied
- About equally satisfied and dissatisfied
- Moderately dissatisfied
- Very dissatisfied

14. Over the past 4 weeks, how **satisfied** have you been with the amount of emotional closeness during sexual activity between you and your partner?

- No sexual activity
- Very satisfied
- Moderately satisfied
- About equally satisfied and dissatisfied
- Moderately dissatisfied
- Very dissatisfied

15. Over the past 4 weeks, how **satisfied** have you been with your sexual relationship with your partner?

- Very satisfied
- Moderately satisfied
- About equally satisfied and dissatisfied
- Moderately dissatisfied
- Very dissatisfied

16. Over the past 4 weeks, how **satisfied** have you been with your overall sexual life?

- Very satisfied
- Moderately satisfied
- About equally satisfied and dissatisfied
- Moderately dissatisfied
- Very dissatisfied

17. Over the past 4 weeks, how **often** did you experience discomfort or pain during vaginal penetration?

- Did not attempt intercourse
- Almost always or always
- Most times (more than half the time)
- Sometimes (about half the time)
- A few times (less than half the time)
- Almost never or never

18. Over the past 4 weeks, how **often** did you experience discomfort or pain following vaginal penetration?

- Did not attempt intercourse
- Almost always or always
- Most times (more than half the time)
- Sometimes (about half the time)
- A few times (less than half the time)
- Almost never or never

19. Over the past 4 weeks, how would you rate your **level** (degree) of discomfort or pain during or following vaginal penetration?

- Did not attempt intercourse
- Very high
- High
- Moderate
- Low
- Very low or none at all

Thank you for completing this questionnaire

Annex 5: S-BIS

BIS/BAS

Each item of this questionnaire is a statement that a person may either agree with or disagree with. For each item, indicate how much you agree or disagree with what the item says. Please respond to all the items; do not leave any blank. Choose only one response to each statement. Please be as accurate and honest as you can be. Respond to each item as if it were the only item. That is, don't worry about being "consistent" in your responses. Choose from the following four response options:

- 1 = very true for me
- 2 = somewhat true for me
- 3 = somewhat false for me
- 4 = very false for me

1. A person's family is the most important thing in life.
2. Even if something bad is about to happen to me, I rarely experience fear or nervousness.
3. I go out of my way to get things I want.
4. When I'm doing well at something I love to keep at it.
5. I'm always willing to try something new if I think it will be fun.
6. How I dress is important to me.
7. When I get something I want, I feel excited and energized.
8. Criticism or scolding hurts me quite a bit.
9. When I want something I usually go all-out to get it.
10. I will often do things for no other reason than that they might be fun.

11. It's hard for me to find the time to do things such as get a haircut.
12. If I see a chance to get something I want I move on it right away.
13. I feel pretty worried or upset when I think or know somebody is angry at me.
14. When I see an opportunity for something I like I get excited right away.
15. I often act on the spur of the moment.
16. If I think something unpleasant is going to happen I usually get pretty "worked up."
17. I often wonder why people act the way they do.
18. When good things happen to me, it affects me strongly.
19. I feel worried when I think I have done poorly at something important.
20. I crave excitement and new sensations.

21. When I go after something I use a "no holds barred" approach.
22. I have very few fears compared to my friends.
23. It would excite me to win a contest.
24. I worry about making mistakes.

Items other than 2 and 22 are reverse-scored.

BAS Drive: 3, 9, 12, 21

BAS Fun Seeking: 5, 10, 15, 20

BAS Reward Responsiveness: 4, 7, 14, 18, 23

BIS: 2, 8, 13, 16, 19, 22, 24

Items 1, 6, 11, 17, are fillers.

The fact that there are three BAS-related scales and only one BIS-related scales was not planned or theoretically motivated. The factors emerged empirically, from an item set that was intended to capture diverse manifestations of the BAS, according to various theoretical statements. It is likely that a broader sampling of items on the BIS side would also have resulted in more than one scale. I do not encourage combining the BAS scales, however, because they do turn out to focus on different aspects of incentive sensitivity. In particular, Fun Seeking is known to have elements of impulsiveness that are not contained in the other scales.

SF-12 Health Survey

This survey asks for your views about your health. This information will help keep track of how you feel and how well you are able to do your usual activities. **Answer each question by choosing just one answer.** If you are unsure how to answer a question, please give the best answer you can.

1. In general, would you say your health is:

- ₁ Excellent ₂ Very good ₃ Good ₄ Fair ₅ Poor

The following questions are about activities you might do during a typical day. Does your health now limit you in these activities? If so, how much?

	YES, limited a lot	YES, limited a little	NO, not limited at all
2. Moderate activities such as moving a table, pushing a vacuum cleaner, bowling, or playing golf.	 ₁	 ₂	 ₃
3. Climbing several flights of stairs.	 ₁	 ₂	 ₃

During the past 4 weeks, have you had any of the following problems with your work or other regular daily activities as a result of your physical health?

	YES	NO
4. Accomplished less than you would like.	 ₁	 ₂
5. Were limited in the kind of work or other activities.	 ₁	 ₂

During the past 4 weeks, have you had any of the following problems with your work or other regular daily activities as a result of any emotional problems (such as feeling depressed or anxious)?

	YES	NO
6. Accomplished less than you would like.	 ₁	 ₂
7. Did work or activities less carefully than usual.	 ₁	 ₂

8. During the past 4 weeks, how much did pain interfere with your normal work (including work outside the home and housework)?

- ₁ Not at all ₂ A little bit ₃ Moderately ₄ Quite a bit ₅ Extremely

These questions are about how you have been feeling during the past 4 weeks.

For each question, please give the one answer that comes closest to the way you have been feeling.

How much of the time during the past 4 weeks...

	All of the time	Most of the time	A good bit of the time	Some of the time	A little of the time	None of the time
9. Have you felt calm & peaceful?	 ₁	 ₂	 ₃	 ₄	 ₅	 ₆
10. Did you have a lot of energy?	 ₁	 ₂	 ₃	 ₄	 ₅	 ₆
11. Have you felt down-hearted and blue?	 ₁	 ₂	 ₃	 ₄	 ₅	 ₆

12. During the past 4 weeks, how much of the time has your physical health or emotional problems interfered with your social activities (like visiting friends, relatives, etc.)?

- ₁ All of the time ₂ Most of the time ₃ Some of the time ₄ A little of the time ₅ None of the time

Patient name:	Date:	PCS:	MCS:
Visit type (circle one)			
Preop	6 week	3 month	6 month 12 month 24 month Other: _____

	MONDAY			TUESDAY			WEDNESDAY			THURSDAY			FRIDAY			SATURDAY			SUNDAY		
WEEK	M		L	M		L	M		L	M		L	M		L	M		L	M		L
1																					
2																					
3																					
4																					
5																					
6																					
7																					
8																					
9																					
10																					
11																					
12																					
13																					
14																					
15																					
16																					
17																					
18																					
19																					
20																					

- ◆ Mark with an "X" in the corresponding box if you have completed the treatment as indicated by your health care professional: M (moisturizer) and/or L (lubricant).
- ◆ If you used some other therapies as D (dilator) or V (vibrator), please fill in.

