To answer the unmet needs previously mentioned, the aim of the current study is to verify the outcomes of sexual and vaginal health in breast cancer women receiving AI, who were experiencing symptoms of GSM, before and after CO2 laser therapy compared to a sham-controlled group.

Specifically, we will compare the following subjective and objective measurements of sexual and vaginal health:

MAIN GOAL: Report an improvement in sexuality:

- Primary outcome: sexual function (FSFI total score)

- Secondary sexual outcomes: resumption sexual activity (sexually active vs non-sexually active), sexual activity frequency (n° sexual activity/week), dyspareunia (VAS), female sexual dysfunction (VAS sexual life distress), sexual dimensions: desire, arousal, lubrication, orgasm, satisfaction and pain (FSFI) and body image (S-BIS)

OTHER OBJECTIVES: Report an improvement on GSM symptoms (efficacy) and quality of life, feasibility and safety of laser therapy in BCS:

- Secondary non-sexual outcomes: quality of life (SF-12). Verify an acidification of the vaginal pH, an improvement in the maturation index and an improvement in the Gloria Backmann Index: Vaginal Health Index. To evaluate toxicity associated with vaginal laser therapy in this population (AEs and SAEs). To determine how many women with the defined patient eligibility will complete all treatments.

METHODS (max 500 words):

DESIGN: Prospective, randomized, double-blind controlled study with two parallel study arms: ARM I: Patients undergo fractional CO2 laser therapy at 5 times points 30 days apart. ARM II: Patients undergo sham laser therapy at 5 time points 30 days apart. After completion of the treatment, patients are followed up at 1 month and 6 months.

RANDOMIZATION PROCESS: A randomization list will be generated in multiple blocks of 2 and 1: 1 ratio with STATA version 15.1 or higher.

STUDY SUBJECTS: Patients treated or undergoing AI for BC in the Breast Cancer Unit of the Hospital Clínic and who present symptoms related to GSM that condition their sexual function and quality of life, despite receiving first-line non-hormonal treatment: regular sexual activity (such as mutual and self-touch masturbation, manual or vibrator stimulation, oral sex, sexual intercourse, massage and other forms of physical intimacy), moisturizers, lubricants, pelvic-floor relaxation techniques and/or dilators. Inclusion and exclusion criteria are summarized in Table 1.

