Annex 1: STUDY STRUCTURE (Table 2):

A) Screening/Recruitment telematic visit (T-2): to select eligible patients and to deliver information sheet and explanation of the project.

B) Screening/Recruitment presential visit (T-1): to perform physical examination and sexual assessment, to confirm eligibility and to sign informed consent.

C) Baseline presential Visit (T0): to fill in baseline questionnaires and to assess sexuality using PLISSIT Model according usual care in our hospital.

D) Treatment visits: T1 (session 1), T2 (session 2), T3 (session 3), T4 (session 4), T5 (session 5): to perform the intervention according previous description.

E) Follow-up visits: T6 (1 month after session 5), T12 (7 months after session 5): to perform physical examination and fill in questionnaires at short and mid-term. Out of timeline project, a visit T24 (13 months after session 5) is planned as usual care practice in our hospital to assess outcomes at long-term follow-up (also approved by our Ethical Committee).

Table 2. Study structure

Endpoint	Instrument	T-2	T-1	T0	T1-T5	T6	T12
Inclusion/exclusion criteria	Checklist database	X					
Trial information	Delivery Written and verbal information Signature Informed consent	X	X				
Baseline characteristics	General Anamnesis BC Anamnesis Sexual Anamnesis Socio-demographic data	X X X X		X			
Physical examination	Gynaecological examination VHI of Gloria Bachmann * ¹ Vaginal pH * ² Maturation index * ³ (vaginal cytology) Liquid cytology (reflex HPV determination) Pelvic floor muscle function		X X X X X			X X X X X	X X X X
GSM symptoms	VAS dispareunia * ⁴ VAS dryness * ⁴ VAS burning * ⁴ ICIQ-IU-SF + CACV			X X X X		X X X X	X X X X
Sexual symptoms	FSFI total score * ⁵ VAS sexual life distress * ⁴			X X		X X	X X
Body image	S-BIS * ⁶			X		X	X
Generic quality of life	SF-12 * ⁷			X		X	X
Intervention	Laser vs sham				X		
Adherence to treatment	Adherence diary				X		
Adverse events	Database/ AEs form				X	X	X
Treatment satisfaction	Likert scale					X	X

*¹Evaluation of the Vaginal Health Index of Gloria Bachmann: An exploration of the lower genital tract will be carried out and the degree of AVV will be assessed through

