([https://www.maturitas.org/article/0378-5122\(95\)00956-6/pdf](https://www.maturitas.org/article/0378-5122(95)00956-6/pdf)). This index subjectively assesses the vagina's staticity, the amount of discharge, the integrity of the epithelium and humidity, along with pH as the only objective criterion. A score of ≤ 15 indicates AVV. It is the Index most used in publications reporting improvement of AVV with the use of lasers.

*²Vaginal vaginal pH: Using a pH test strip, colorimetric analysis of the pH of the vaginal discharge is performed.

*³Maturative Index: Using vaginal cytology, the percentage of parabasal, intermediate and superficial cells is calculated, allowing us to calculate the epithelial thickness indirectly.

*⁴ Visual Analog Scale (VAS): Evaluates 3 symptoms of AVV: dyspareunia, dryness and burning. Score from 0 to 10 (unbearable symptom). Symptoms are considered moderate from ≥ 4 .

*⁵ Female Sexual Function Index (FSFI): Generic sexual questionnaire validated for cancer survivors. We used the 19-item self-reported Spanish validated questionnaire to assess 6 sexual dimensions (desire, arousal, lubrication, orgasm, satisfaction and pain) and the global sexual function. Score ranges from 1,6 to 36, with the higher score indicating a better sexual Function. Function. A cut-off value of ≤ 26.55 indicates risk of sexual dysfunction, however, it could inflate female sexual dysfunction rates in those women whose sexual activity frequency is lower than once a month or in non-sexually active women. (<https://scielo.conicyt.cl/pdf/rchog/v69n2/art06.pdf>)

*⁶ Body Image Scale-Spanish version (S-BIS): Assesses 10 domains of body image in 10 questions and is applicable in patients with any type of cancer and different therapeutic regimens. The total score ranges from 0 to 30. The higher the score, the greater the concern regarding body image. (<https://www.ncbi.nlm.nih.gov/pubmed/25135839>).

[figure not shown]
*⁷ Quality of life Short Form 12 (SF-12): It consists of 12 items from the 8 dimensions of the SF-36 Physical Function (2), Social Function (1), Physical Role (2), Emotional Role (2), Mental health (2), Vitality (1), Body pain (1), General Health (1). (http://www.ser.es/wp-content/uploads/2015/03/SF12_CUESTIONARIO.pdf)

VVA: Severity classification / assessment Vaginal Health Index (Gloria Bachmann)

Score	1	2	3	4	5
Elasticity	none	poor	fair	good	excellent

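### The form annexed as the body image scale is a different questionnaire (BIS/BAS), and the weekly sexual-activity outcome has no stated collection at T6 or T12

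*Combined protocol and SAP*

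**What the plan says.** **Body image.** AIMS lists body image, measured by the S-BIS, among the secondary sexual outcomes. Table 2 in Annex 1 schedules it at T0, T6 and T12. Footnote 6 defines the scale: "Assesses 10 domains of body image in 10 questions" and "The total score ranges from 0 to 30", with higher scores meaning more concern. The form under the heading Annex 5: S-BIS is titled BIS/BAS. It has 24 statements, each answered 1 to 4. Its key assigns items to three BAS subscales, for example "BAS Reward Responsiveness: 4, 7, 14, 18, 23", and one BIS subscale, and adds "Items 1, 6, 11, 17, are fillers". A note after the key says "I do not encourage combining the BAS scales".

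**Activity frequency.** AIMS also lists "sexual activity frequency (n° sexual activity/week" as a secondary outcome, and the SUMMARY repeats activity frequency. Table 2 has no row for it. The sexual history appears only under baseline characteristics, in the group "General Anamnesis BC Anamnesis Sexual Anamnesis Socio-demographic data". Annex 1 gives the purpose of the T6 and T12 visits as "to perform physical examination and fill in questionnaires at short and mid-term".

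**The concern.** The BIS/BAS and the Body Image Scale share an abbreviation but measure different things. The BIS/BAS subscales are named for drive, fun seeking, reward responsiveness and BIS. Its nearest approaches to appearance, items on dress and on haircuts, are both unscored fillers. If staff used Annex 5 as printed, the trial would have no body-image score and a temperament score could be filed under the S-BIS label. The answers could not be converted afterwards.

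For activity frequency, STATISTIC ANALYSIS sends repeatedly measured variables to MMRM or GEE. Both need post-baseline values, and the plan does not say where a weekly count at T6 or T12 would come from. A count not asked for at the visit cannot be reliably recovered later.

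**Working it through.** **1. Footnote 6 on its own terms.** Item scoring is not stated. Assuming 10 equally weighted questions scored 0 to 3, the range is 10 × 0 = 0 to 10 × 3 = 30. The stated range is reproduced, so the footnote is consistent with itself.

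**2. What Annex 5 can produce.** Each item is answered 1 to 4. Reverse-scoring maps 1-4 onto 4-1, so the ranges do not change.

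| Group | Items | n | Minimum (n × 1) | Maximum (n × 4) |
|---|---|---|---|---|
| BAS Drive | 3, 9, 12, 21 | 4 | 4 | 16 |
| BAS Fun Seeking | 5, 10, 15, 20 | 4 | 4 | 16 |
| BAS Reward Responsiveness | 4, 7, 14, 18, 23 | 5 | 5 | 20 |
| BIS | 2, 8, 13, 16, 19, 22, 24 | 7 | 7 | 28 |
| Fillers | 1, 6, 11, 17 | 4 | not scored | not scored |

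Scored items: 4 + 4 + 5 + 7 = 20. With the 4 fillers the total is 24, and every item from 1 to 24 is used exactly once. All scored items summed would run 20-80; all 24 items, 24-96. Combining subscales of 4, 4, 5 and 7 items gives totals of 8, 9, 11, 12, 13, 15, 16 or 20 items, never 10. No score starts at 0, and the form's own note advises against combining the BAS scales. The 10-question, 0-30 total cannot be obtained from this form.

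**3. Search for a weekly activity count at T6 or T12.**

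- *Table 2:* the marks for the baseline-characteristics group fall at T-2 and T0. At T6 and T12 the schedule holds the physical examination items, symptom VAS scales, the two urinary questionnaires, FSFI, distress VAS, S-BIS, SF-12, adverse events and satisfaction. None is an activity count.
- *FSFI form:* 8 of 19 items (1, 3, 6, 7, 9, 11, 17, 18) ask how often something was experienced, but the answers are proportions of occasions. Items 3-14 (12 items) include a no-activity option, items 17-19 (3 items) a no-attempt option, and items 1, 2, 15 and 16 (4 items) neither: 12 + 3 + 4 = 19. Items asking for a number: 0. A woman active once in four weeks and one active 20 times can give identical answers. Active versus non-active status can be derived from these options; a weekly number cannot.
- *Adherence diary:* it records moisturizer and lubricant use, plus dilator or vibrator use. Table 2 marks it only at T1-T5. It has 20 weekly rows, 20 × 7 = 140 days. Assuming it starts at session 1 and months last 30 days, session 5 is on day 4 × 30 = 120, T6 on day 120 + 30 = 150 and T12 on day 120 + 7 × 30 = 330. It would end before both visits.
- *VAS:* footnote 4 defines it as a 0-10 symptom score, so it cannot supply a count.

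Follow-up visits with a stated source for the weekly count: 0 of 2.

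**The case against.** On body image, the plan names the right scale everywhere it specifies the measure: glossary, summary, outcome list, Table 2 and footnote 6. The annexes also look like reference copies. The FSFI is printed in English although footnote 5 says the Spanish version is used. The SF-12 copy carries unrelated visit boxes, and the BIS/BAS copy includes its scoring key and its developer's comments. A figure after footnote 6 is not shown and may be the correct scale. This makes administration of the wrong form less likely, and the harm is conditional on that happening. The contradiction remains: whatever the missing figure shows, Annex 5 prints another instrument under the S-BIS label.

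On activity frequency, Table 2 is broken in the available text, the diary has one unlabelled column, and the Annex 3 VAS form has no visible content. Usual-care PLISSIT assessment or the study database, whose content is not given, might record a count. What stands is that this is a gap in specification, not proof that nothing will be collected. No broken cell could place the sexual history at T6 or T12, and the diary's unlabelled column could not cover T12.

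Footnote 5's remark that infrequent activity can inflate dysfunction rates at the FSFI cut-off is only minor support. AIMS ties the dysfunction outcome to the distress VAS, and the FSFI no-activity option already approximates the condition that footnote 5 describes.

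**Conclusion.** Both parts hold. Annex 5 contradicts footnote 6: 24 items against 10, and four separate subscales against a single 0-30 total. If Annex 5 is administered, 0 of 3 scheduled assessments yield a body-image score. The weekly sexual-activity count has a stated source at 0 of 2 post-baseline visits. The first result needs no assumption beyond the annex being used as printed. The second rests on the schedule and forms as published, since the database is not shown.

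The effect is confined to two secondary outcomes. The primary FSFI total is scheduled at T0, T6 and T12 with its form attached, and sample size, randomisation and the primary analysis are untouched. This should be fixed before data collection, but it does not threaten the main result.

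**What to change.** Before the first baseline visit:

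1. Replace Annex 5 with the 10-question, 0-30 Spanish Body Image Scale that footnote 6 describes, and check that the case report form and database use the same instrument.
2. Add a Table 2 row at T0, T6 and T12 for the number of sexual activities per week, with a stated recall period, for example 4 weeks to match the FSFI. State which definition of sexual activity applies, because the FSFI instructions and the STUDY SUBJECTS section give different lists.
3. Optionally, state that active versus non-active status is derived from the FSFI no-activity answers, or ask it in the same row. This is a clarification; that outcome is not otherwise missing.

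The cost is one annex swap, one schedule row and one question at visits that already take place.
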